Plication of Fascia Transversalis and Its Role in Reduction of Seroma Formation Post Laparoscopic Transabdominal Preperitoneal Repair of Direct Inguinal Hernia

A Thesis Submitted For Partial Fulfillment of MSc Degree of General Surgery

By

[name] [name]

Ethical Approval Number: MS 204-2024

Supervisors

[name]. [name]
Professor of General Surgery
Faculty of Medicine, Cairo University

[name] [name]
Lecturer of General Surgery
Faculty of Medicine, Cairo University

[name] [name]
Lecturer of General Surgery
Faculty of Medicine, Cairo University

Faculty of Medicine
Cairo University
2025

Statistical Analysis

Data are analyzed using SPSS version 21. Descriptive statistics are presented as means with standard deviation for continuous variables and frequencies with percentages for categorical variables. Comparisons between groups are made using:

- Chi-square test or Fisher 's exact test for categorical data.
- Student ' s t-test for normally distributed continuous variables.
- Mann-Whitney U test for non-normally distributed data.
- Paired t-test for preoperative and postoperative comparisons within each group.
- Pearson or Spearman correlation tests to assess relationships between variables.

A p-value < 0.05 is considered statistically significant.

Ethical Considerations

This study is conducted in accordance with the Declaration of Helsinki and is approved by the Institutional Review Board (IRB) of Cairo University. Written informed consent is obtained from all participants prior to enrollment. Patients' confidentiality is maintained, and their data are anonymized. No financial incentives are provided, and participation is voluntary. Potential risks, including coagulation alterations and allergic reactions, are clearly explained to the patients.

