Patients will randomly allocated (1:1) in two groups, group A and group B, one week before surgery by the coordinating researcher via computer-generated variable block randomization software by Ciwit BV (Castor EDC©). The patient, surgical team, and anesthesia team were blinded for treatment allocation. The coordinating researcher and hospital pharmacologist were unblinded to properly prepare the infusion bags for each individual patient. Both were not involved in the surgical procedure nor in the follow-up. Patients in each group will have proper history taking, routine pre-operative assessment. The intervention group (B) will receive a single dose of 1500-mg TXA (Cyklokapron©) during the induction of the procedure. TXA will be administered intravenously, dissolved in 100-ml sodium chloride (NaCl) 0.9% in a time frame of 15–30 min, with a maximum of 100 mg/min. The control group (A) will receive a placebo during the induction of the procedure. The placebo infusion contains 100-ml NaCl 0.9%, which will be administered similarly. Both groups will be operated on within the same range of blood pressure. Assessment of intra-operative bleeding will be through the number of clips used on the staple line. To determine postoperative hemoglobin levels, a blood sample (one EDTA tube) will be obtained at day one postoperatively by venipuncture and analyzed in the hospital's clinical chemistry laboratory according to standard procedures. Patients will be discharged at day 3 post-op, on anti-coagulant 40mg/24H for two weeks. Follow up will be done after 30 days. Duple will be done to assess the incidence of DVT.

- **Intervention:**

- Diagnostic intervention (please describe):
- Therapeutic intervention (please describe):
- No intervention

- **Does the research involve?**

- Human participants
- Biological samples/Tissues
- Identifiable private data/Information

- **Type of consent of study participants:**

- Written consent
- No consent needed (Please justify)

- **Potential risks:**

(Please mention all risks involved even mild ones as pain, discomfort, chance of infection or psychological effects)

- 1-
- 2-
- 3-

- **Confidentiality of data:** (Please explain how privacy and confidentiality of data and records will be maintained)

9- Study outcomes:

- **Primary outcomes** (Most important measurable outcomes)

- 1- Number of cases of bleeding in each group either intra-operative or post-operative
- 2- definition of bleeding: hemoglobin drop >1

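### The SAP's only pre/post method is a within-arm paired t-test, nothing adjusts for pre-operative haemoglobin, and the protocol does not say which pre-operative value counts: a minor, cheap improvement

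*SAP*

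**What the plan says.** The SAP, Statistical Analysis, opens its list of methods with "Comparisons between groups are made using". The list holds chi-square or Fisher for categorical data, Student's t for normally distributed continuous data, "Mann-Whitney U test for non-normally distributed data", then "Paired t-test for preoperative and postoperative comparisons within each group", and finally Pearson or Spearman correlation. No regression, ANCOVA or other covariate adjustment appears. Section 11 of the protocol (Statistical analysis) holds only the template prompt.

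The protocol's primary outcome (section 9) is the number of bleeding cases per group, intra-operative or post-operative, with "definition of bleeding: hemoglobin drop >1". No unit is given. Section 8, Methodology in details, fixes the later measurement: "To determine postoperative hemoglobin levels, a blood sample (one EDTA tube) will be obtained at day one postoperatively". For the earlier one it says only "Patients in each group will have proper history taking, routine pre-operative assessment". Haemoglobin is not named there and no time is stated. Continuous haemoglobin is not a primary or secondary outcome in section 9.

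The SAP's title page reads "Plication of Fascia Transversalis and Its Role in Reduction of Seroma Formation Post Laparoscopic Transabdominal Preperitoneal Repair of Direct Inguinal Hernia", and the SAP never mentions haemoglobin. Its Ethical Considerations would, however, fit a TXA trial: "Potential risks, including coagulation alterations and allergic reactions, are clearly explained to the patients".

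**The concern.** A paired t-test within an arm asks whether that arm's mean changed. Some fall in haemoglobin after surgery is expected in both arms, so the answer says little about TXA. The between-arm difference in haemoglobin, adjusted for where each patient started, is the more useful quantity. The primary outcome already requires both measurements, yet no listed method delivers that estimate.

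The second gap lies in the protocol and stands whichever SAP applies. A fall of more than 1 is measured from a pre-operative value that the protocol does not identify. If that value comes from different times in different patients, the extra noise misclassifies bleeding status and weakens the primary comparison. Allocation is one week before surgery, so as written the value could predate or follow allocation. Blinding makes a systematic difference between arms unlikely, so the issue is noise rather than bias.

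**Working it through.** The plan gives no figure to reproduce: section 10 of the protocol (Sample size and technique) holds only the template prompt. Every SD, correlation, effect and sample size below is an assumption, and haemoglobin is taken in g/dL. The only document inputs are 1:1 allocation, the 0.05 significance level (two-sided assumed), the threshold of 1, and the background figure of up to 11% for bleeding that needs intervention.

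**1. Precision of a between-arm haemoglobin estimate.** Let r be the pre/post correlation, SD 1.3, n = 50 per arm. Ignoring the small term for chance baseline imbalance:

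- ANCOVA half-width = t(97) × 1.3 × √(2(1 − r²)/50)
- Change-score half-width = t(98) × 1.3 × √(4(1 − r)/50)

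| r | ANCOVA | Change score |
|---|---|---|
| 0.5 | 0.447 | 0.516 |
| 0.7 | 0.369 | 0.400 |
| 0.8 | 0.310 | 0.326 |

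The variance ratio, ANCOVA to change score, is (1 + r)/2, that is 0.75, 0.85 and 0.90.

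**2. Power depends on how TXA acts.** Simulation, 20,000 replicates per cell, 50 per arm; chi-square is applied to a fall of more than 1.

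| Scenario | Chi-square | Change-score t | ANCOVA |
|---|---|---|---|
| Uniform shift (mean fall 1.0 vs 0.6), r = 0.5 | 24% | 33% | 42% |
| Uniform shift, r = 0.7 | 36% | 50% | 56% |
| Uniform shift, r = 0.8 | 49% | 67% | 72% |
| Discrete bleeds, 25% vs 8% | 59% | 55% | 54% |
| Discrete bleeds, 20% vs 5% | 58% | 54% | 53% |
| Discrete bleeds, 11% vs 3% | 26% | 25% | 25% |

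In the discrete-bleed scenarios non-bleeders fall by 0.3 (SD 0.35) and bleeders by 2.8 (SD 0.8). ANCOVA gains over the change score only under the uniform shift. With discrete bleeds it ties the change score and does not beat chi-square.

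**3. Baseline timing noise.** Add random error of SD u to the pre-operative value in both arms. With bleeder share s, the probability of a fall of more than 1 is

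s × Φ((2.8 − 1)/√(0.8² + u²)) + (1 − s) × Φ((0.3 − 1)/√(0.35² + u²)).

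At u = 0 this is s × 0.988 + (1 − s) × 0.023. For s = 0.25 it gives 0.264, and for s = 0.08 it gives 0.100.

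| u (g/dL) | Fall >1, placebo vs TXA | Chi-square power, 50 per arm |
|---|---|---|
| 0 | 26% vs 10% | about 59% |
| 0.2 | 28% vs 12% | about 54% |
| 0.3 | 29% vs 14% | about 48% |
| 0.5 | 34% vs 19% | about 38% |

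Simulation and exact enumeration of the two binomials agree on these powers to within about a point. In the uniform-shift model at r = 0.7 the loss is milder: 36% falls to 34% at u = 0.3 and 30% at u = 0.5. Intra-operative bleeding, which the protocol assesses by clips, is not modelled, so these figures concern only the haemoglobin component of the primary outcome.

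**4. If the two paired p-values were contrasted.** With no TXA effect and within-arm power p, exactly one arm is significant with probability 2p(1 − p).

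| Mean fall | SD of change | n per arm | Exactly one arm significant |
|---|---|---|---|
| 1.0 | 1.3 | 50 | 0.0008 |
| 1.0 | 1.3 | 25 | 0.08 |
| 0.5 | 1.0 | 25 | 0.44 |
| 0.4 | 1.3 | 50 | 0.49 |

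The range is therefore 0 to about 50%, depending entirely on within-arm power.

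**The case against.** The strongest reply is that nothing needed for the primary question is missing. Chi-square or Fisher covers the binary primary outcome, that outcome already uses the fall from baseline, and an unadjusted comparison is valid in a 1:1 randomised trial. Student's t or Mann-Whitney could be applied to haemoglobin between arms. Continuous haemoglobin is not a listed outcome, and ANCOVA brings no power gain when TXA prevents discrete bleeds. All of this stands, and it is why the point is minor and the ANCOVA only supporting.

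A reader might infer that the trial will judge TXA by setting one arm's paired p-value against the other's. The SAP plans no such contrast. Its between-group heading also covers correlation tests, so it introduces a loosely drafted general list. That the paired test is meant for haemoglobin is itself an inference, since the SAP never names haemoglobin and carries another study's title.

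Two further limits stand. The timing-noise SDs have no anchor in the documents, and at 0.2 the power loss is only about 5 points. The protocol places surgery between January and August 2024 and the SAP title page is dated 2025, so a new fixed-time sample may no longer be possible and an ANCOVA added now may be post hoc.

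The objection does not remove the two textual facts: no listed method gives a baseline-adjusted comparison of the arms, and the baseline value for the bleeding definition is not identified.

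**Conclusion.** The point holds as a minor improvement to a supporting analysis and to one definition. It is not a flaw in the primary test. A reader might go further and conclude that the plan has no valid between-arm analysis, or that its primary result would be misleading. The documents do not support either, because valid unadjusted tests are listed and the paired test is not offered as evidence of a TXA effect.

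The gain from ANCOVA is modest. Its intervals are about 5% to 13% narrower than those from change scores at correlations 0.8 to 0.5 (0.310/0.326 = 0.95; 0.447/0.516 = 0.87), under the assumed normal model. The baseline rule matters more, because it reaches the primary outcome directly. How much power it protects depends on timing noise that the documents do not let anyone estimate. Confidence is medium, mainly because it is uncertain whether this SAP belongs to the trial.

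**What to change.** First, the sponsor confirms whether the SAP, with its hernia-study title page, is the plan for this trial. If it is not, the SAP line below goes into the correct document.

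1. In the SAP, replace the paired t-test bullet with: *Pre- and post-operative haemoglobin will be summarised by group as description. As a supporting analysis, day-1 haemoglobin will be compared between groups by ANCOVA with treatment group and pre-operative haemoglobin; the adjusted difference (TXA minus placebo) will be reported with its 95% CI.*
2. In the protocol, state one rule, the same in both arms, for which recorded pre-operative haemoglobin is used for the bleeding definition and for the ANCOVA, for example the last value before induction. If data are already collected, this is a selection rule among recorded values, best fixed without sight of allocation, and the ANCOVA is labelled post hoc.

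The binary outcome and its chi-square or Fisher test stay primary. The cost is one bullet and one protocol sentence, with no new variable, since the primary outcome already needs a pre-operative value. The downside is that ANCOVA estimates a mean difference, a different quantity from the proportion who bleed, and does not raise the power of the primary test.
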